## 4. Participants, Population & Selection

### 4.1 Setting

Polana Caniço, peri-urban Maputo, Mozambique: a health- and demographic surveillance system (HDSS) covering a population of 15,393, in the catchment area of the Polana Caniço General Hospital (PCGH), one out of two COVID-19 referral facilities in Maputo.

The population in peri-urban Polana Caniço is relatively representative of the increasingly urban population in Southern Africa, having young and mobile inhabitants. Moreover, the population suffers increasingly from non-communicable diseases, and prevalence of HIV and active tuberculosis is presumed to be important. Research gaps on COVID-19 transmission dynamics include whether the reproduction number could be different in such different (eg. younger) population. Also, the potential association between (uncontrolled) HIV infection or (active) tuberculosis and COVID-19 infection and severe disease, needs to be elucidated.

The Polana Caniço-HDSS has been established since 2017. In total, as of time of writing, 2108 households (defined as residents of the same building, sharing a cooking area) have been enrolled in the HDSS. All members residing in the household for at least 3 months (infants, children, adults, elderly) are enrolled in the HDSS. Surveillance rounds are currently carried out six-monthly. Demographic and health indicators collected in each surveillance round include but are not limited to: fertility/birth rate, mortality/cause of death, migration, disease cases, trauma and violence, socioeconomic status, water and sanitation facilities, risk factors for the acquisition of chronic diseases, women's health and family planning, immunization, risk behaviours and cultural practices related to the transmission of STI (including HIV and syphilis). Testing for HIV and syphilis is planned to be added as part of the surveillance rounds, from October 2020 onwards. Data on births, deaths, internal and external migration, pregnancies and their outcomes, and any other relevant events from a demographic perspective, are continuously reported by community key informants and confirmed through home visits.

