An **age-stratified random sample** of that population will be selected for the **repeated sero- and social mixing survey**. By age stratum (0-17 years; 18-50 years; >50 years) we randomly select 800 individuals (simple random sample per age stratum; 2400 in total) from the Polana Caniço HDSS population (regardless of infection or disease status or history), from whom during home visits dried blood spots will repeatedly be collected at 0, 3, 6 and 12 months, vaccination status against COVID-19 will be recorded, and who will be asked to respond to a social mixing questionnaire. A HDSS sampling frame of all individual participants in the HDSS with socio-demographic data and unique identifiers, is available, and will be used to select a simple random sample of individuals by age group.

When a member of a household with no prior widespread transmission (see exclusion criteria) tests SARS-CoV-2 positive, we will revisit the household twice for a household transmission investigation: as soon as possible after the result of the household index case (baseline), and once again one month after symptom onset of the household index case. An initial contact report form will be filled in as soon as possible, ideally within 24 hours, after laboratory confirmation of the primary case in the household. Respiratory and dried blood spot samples will be collected of everyone considered resident (as defined by the HDSS) in the household and who has been in contact with the SARS-CoV-2 positive individual, regardless of age and presence or absence of symptoms. Respiratory samples will be analysed by RT-PCR for SARS-CoV-2 to assess presence of virus and viral load. The dried blood spots for serology on the Luminex assay. Data will be collected on household exposures of contacts and vaccine receipt. Symptomatic household contacts will be tested whenever symptoms appear, as part of the population-based surveillance. This is planned for upto 100 household index cases.

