All HDSS households will be visited by a trained HDSS interviewer to present the study and ask for informed consent (i) by the household head for the population-based surveillance and (ii) by the individuals selected for the age-stratified serial sero-survey. During this same visit, if the household head consented, the demographics data (baseline household visit form) will be verified and updated. A study household card with unique IDs of each household member will be provided (code containing the housing block, household id and sequential household member number). Household members will be sensitized on symptoms related to COVID-19, are asked to keep track of possible symptoms they may develop, and inform the study team by phone if a household member has a respiratory symptom, loss of smell or taste, so that upon assessment he/she can be asked to be swabbed for virological testing. In case a household member presents with symptoms which classify him/her as a possible case, a separate individual informed consent procedure for nasal swabbing will have to be performed prior to sampling. This ICF covers sampling for the first episode and any subsequent episode during the study period when nasal sampling would be indicated. Also during the baseline household visit, if full informed consent was provided (both for surveillance by the household head and for the sero- and social mixing survey by the individual household member), individual household members selected for the sero-survey will be asked for a baseline dried blood spot sample on filter paper, by administering a few blood drops through a finger prick.

Every two weeks a trained interviewer from the HDSS team will do calls to the head of the household or his representative, where during the call he will fill out a questionnaire (Household follow-up visit form) recording any respiratory symptoms, fever or other indicative sign of COVID-19 (at the time of the phone call, or in the last two weeks, if these symptoms go away), vaccination against COVID-19, and medical appointments that any family member has had.

Meanwhile (if applicable), demographic changes or changes in the chronic medical conditions of family members will be recorded. If a family member reports a respiratory sign or loss of smell or taste, with or without fever (possible case), a trained interviewer will do a home visit to this household.

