The repeated sero-survey, collecting dried blood spots through a finger prick, will be added to the biweekly household visits at 3, 6 and 12 months after COVID-19 local transmission is confirmed. During four other biweekly household visits, the participants selected for the sero-survey will also be interviewed on contact and mobility patterns during the previous day, and uptake of COVID-19 control measures, using the 'Social mixing questionnaire'. Its timing will depend on the stage of the outbreak:

1. shortly after the baseline interview (second visit),
2. when local transmission is well established and the number of new cases is increasing,
3. a month after an initial peak, when the number of new cases is decreasing,
4. during the final study visit.

Table 4 . Forms completed during each study activity

Planned activities	Sample size	Research form
Baseline household visit	15393 individuals (2108 households)	
 
· Informed consent form for population-based COVID-19 surveillance (with household head)
 
· Informed consent form for serial sero-survey (with selected individual)
 
· Baseline household visit form
 

Active syndromic population surveillance	15393 individuals (2108 households) visited every 2 weeks	
 
· Household follow-up visit form
 

Swabbing & PCR testing of symptomatic individuals	possible cases from the surveillance population; initially pooled testing of possible cases; when >50 confirmed cases per week, switch to PCR testing of 1 in 10 suspected cases	
 
· Possible case report form
 
· Possible case lab request and result form
 

Follow-up of PCR confirmed cases at day 28 and day 56 past symptom onset	PCR confirmed cases from the surveillance population	
 
· Confirmed case follow-up form
 

Age-stratified sero-survey at 0, 3, 6, 12 months	2400 individuals/serum samples per round (800 per age group <18yo, 18-50 yo, >50yo NOTE: this is budget dependent, pending cost of	
 
· Sero-survey form
 
· Sero-survey lab request and result form
 

	assay, might be decreased to 1600, spread over two age strata)	
Social mixing survey	the same 2400 individuals selected for the sero-survey; during different HH visits than sero-survey visits	· Social mixing questionnaire

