We will derive brand-specific total vaccine effectiveness against infection and against disease, in respectively a case-cohort design and a cohort design. Total vaccine effectiveness is the protection of vaccinees due to direct effects and added protection of vaccinees owing to vaccination of their neighbors or contacts, while overall vaccine effectiveness considers protection of an entire population, irrespective of the vaccination status of its individual members, due to the combination of total protection and protection of non-vaccinees due to vaccination of their neighbors or contacts (Ali et al 2015). To derive total vaccine effectiveness against infection, we will compare the proportion of sero-survey participants who seroconverted in the past 3 months among vaccinated against the proportion in non-vaccinated, adjusting for age and sex and other confounders. To derive total vaccine effectiveness against disease, we will compare the odds of vaccination among symptomatic confirmed SARS-CoV-2 cases detected through the population-based surveillance with the odds of vaccination among sero-survey participants who did not seroconvert in the past 3 months, in a case-cohort design. We will also explore overall vaccine effectiveness against disease using regression models comparing housing blocks with different levels of vaccination coverage among sero-survey participants.

We will estimate the conventional data-based secondary attack rate, which is the proportion of seroconversion among identified household contacts. However, these are not necessarily all secondary infections from the household index case, and could be tertiary. Therefore we will also derive a model-based secondary attack rate, estimating the number of actual secondary infections of the household index case. To do so, we could use a chain-binomial statistical model, as described by Jing et al (doi:10.1016/S1473-3099(20)30471-0), with an expectation-maximisation algorithm to account for (a) uncertainty in the infection time of asymptomatic infections, for (b) an incubation and infectious period distribution, as described in literature, and consider (c) the timing of symptom onset in

symptomatic household contacts and (d) the age-specific proportion of asymptomatic infections as estimated from the active population-based surveillance and sero-survey.

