## 7.2 Sample size and power

Assuming a 40% annual attack rate, 50% symptomatic infections (cases), 2% overall case fatality risk, of which 90% are identified by the active population surveillance, 2790 COVID-19 cases and 56 deaths will be identified through the study period. The average incidence rate of the HDSS population would then be 1.50 cases per 100 person months with lower and upper 95% confidence interval limits 1.45 and 1.56. The overall case fatality risk would have as lower and upper 95% confidence interval limits at 1.53 and 2.58%.

To determine the infection attack rate from a simple random population sample of three age strata (comparable in size), with +/-3% confidence limits, 95% confidence interval, assuming the attack rate may reach 40% towards the end of the study period, samples from 800 individuals per age stratum per round will need to be collected.

Assuming the household secondary attack rate to be close to 17% (Fung et al, Clin Infect Dis, 2020) and a median household size of 7.3 (based on HDSS data), a 5% confidence limit and a design effect of 3, 642 household members will need to be enrolled, or 100 households. The WHO also recommended to include 100 households in household transmission investigations.

Assuming 20% vaccination coverage among the 2400 sero-survey participants, 5% of sero-conversion over 3 months and 10% of seroconversion over 6 months, a 95% two-sided confidence interval and an anticipated crude total vaccine effectiveness of 50%, there will be 66% power to observe this effect after 3 months and 97% power after 6 months.

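### Overall vaccine effectiveness is to be regressed on block coverage from the 15.6% sero-survey sample, although the household form allows coverage of all enrolled members; sampling error attenuates the coverage slope.

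*Combined protocol and SAP*

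**What the plan says.** Section 7.1 (Methods) says that overall effectiveness against disease will be explored with regression models "comparing housing blocks with different levels of vaccination coverage among sero-survey participants". It defines overall effectiveness at the level of the whole population, whatever each member's own vaccination status. Section 2 and the Synopsis list overall effectiveness among the secondary objectives.

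The sero-survey sample is set in Section 4.2: "we randomly select 800 individuals (simple random sample per age stratum; 2400 in total". Sampling is random within age stratum, not within block, so the number sampled per block is left to chance. Table 4 in Section 5.1 adds that, for budget reasons, the sample "might be decreased to 1600, spread over two age strata". Section 4.1 describes the HDSS as "covering a population of 15,393, in the catchment area" of the local hospital.

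Section 5.1 also describes the two-weekly household follow-up questionnaire, answered by the household head or a representative. It records "vaccination against COVID-19, and medical appointments that any family member has had". Each member's identifier is a "code containing the housing block, household id and sequential household member number".

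The opening paragraph of Section 7.1 says that sero-survey results will be adjusted for the age-stratified sampling. Nothing in the plan addresses error in estimated block coverage.

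**The concern.** In this regression the exposure is a block-level proportion. If each block's coverage is estimated from a few dozen sampled residents, part of the apparent difference between blocks is chance. In expectation, chance error in an explanatory variable flattens the fitted slope, and a larger number of sampled people overall does not help if the number per block stays small. The age adjustment addresses who is over-represented, not how few people are sampled in each block.

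A flattened slope could be read as little or no population-level benefit from vaccination. The problem is largely avoidable, because the plan already collects vaccination status on a much wider base, in the same surveillance population that supplies the disease outcomes.

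**Working it through.** **The plan's own figure.** No power or precision is stated for the block analysis. The only vaccine-effectiveness calculation, in Section 7.2, concerns total effectiveness: "Assuming 20% vaccination coverage among the 2400 sero-survey participants", with "5% of sero-conversion over 3 months and 10% of seroconversion over 6 months", effectiveness of 50%, and stated power of 66% and 97%. Taking 0.20 × 2400 = 480 vaccinated and 1920 unvaccinated, with 5% vs 2.5% and then 10% vs 5%, two-sided 0.05:

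- Fisher's exact test gives 67.7% and 95.6%.
- The continuity-corrected chi-square test gives 64.3% and 95.2%.

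Both are within 2 points of the stated values, so that calculation is not in dispute. It does not cover overall effectiveness.

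**Inputs for the block analysis.**
- From the documents: n = 2400, N = 15,393, coverage c = 0.20. Sampling fraction f = 2400/15,393 = 0.156.
- Assumed, because the documents do not give them: number of blocks B, and true between-block SD of coverage S. Blocks are taken as equal in size.

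**Formulas.** Sampled per block: m = 2400/B. Sampling variance of block coverage, with finite-population correction: v = c(1 − c)/m × (1 − f). Share of the slope retained: λ = S²/(S² + v).

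**30 blocks.** m = 80. v = 0.16/80 × 0.844 = 0.00169, an SE of 4.1 points.
- S = 5 points: λ = 0.0025/(0.0025 + 0.00169) = 0.60
- S = 10 points: λ = 0.0100/(0.0100 + 0.00169) = 0.86

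**100 blocks.** m = 24. v = 0.16/24 × 0.844 = 0.00563, an SE of 7.5 points.
- S = 5 points: λ = 0.0025/(0.0025 + 0.00563) = 0.31
- S = 10 points: λ = 0.0100/(0.0100 + 0.00563) = 0.64

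| Blocks (assumed) | Sampled per block | SE, points | λ, S = 5 | λ, S = 10 | λ, S = 15 |
|---|---|---|---|---|---|
| 30 | 80 | 4.1 | 0.60 | 0.86 | 0.93 |
| 75 | 32 | 6.5 | 0.37 | 0.70 | 0.84 |
| 100 | 24 | 7.5 | 0.31 | 0.64 | 0.80 |
| 150 | 16 | 9.2 | 0.23 | 0.54 | 0.73 |

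**Check by simulation.** A simulated Poisson block regression gave slope ratios of 0.61 / 0.87 / 0.94 with 30 blocks, 0.43 / 0.72 / 0.86 with 75 and 0.31 / 0.57 / 0.75 with 150 (S = 5 / 10 / 15). The pattern is the same, with somewhat less loss than the formula at small S and many blocks. On the effectiveness scale, a true 50% (100% vs 0% coverage) was estimated as:
- 30 blocks: 35% / 45% / 48%
- 75 blocks: 26% / 39% / 45%
- 150 blocks: 19% / 32% / 40%

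With coverage taken from all members of each block, the simulation returned 50%. That run contained no reporting error.

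**Effect of age weighting.** With 75 blocks and S = 10, weighting changed the simulated ratio from 0.72 to 0.69. Weighting adds variance, so it does not cure the attenuation.

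**If the sero-survey is cut to 1600.** f = 1600/15,393 = 0.104. With 30 blocks, v = 0.16/53.3 × 0.896 = 0.00269, so λ = 0.48 (S = 5) or 0.79 (S = 10). Using only two strata could also leave one age group out of the coverage measure, which this arithmetic ignores.

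**The case against.** Several points against pressing this are fair.

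- **It is exploratory.** No power claim or decision rests on it. This stands and keeps the priority low, but overall effectiveness remains a listed secondary objective and the remedy is cheap.
- **The wider data are weaker per person.** Household heads or their representatives report for everyone, mostly by phone, whereas the sero-survey records vaccination status for selected individuals at home visits. This stands. All-member coverage removes sampling error but brings proxy-report error of unknown size, possibly differing by block. One might infer that it removes nearly all the error; the documents do not support that.
- **The age imbalance is handled.** A reader might infer that block coverage will also be distorted because the sample over-represents some ages. The documents do not support this as a separate fault: Section 7.1 promises adjustment for age-stratified sampling, Section 7.2 calls the strata comparable in size, and no age distribution is given.
- **Net bias is not determined.** One might conclude that overall protection will be understated. Attenuation holds in expectation with all else equal, but a comparison of blocks is also open to block-level confounding in either direction.
- **The loss may be small.** With 30 blocks and S = 15, λ is 0.93. Omitting the finite-population correction would make the loss look larger (0.56 and 0.83 with 30 blocks, 0.27 and 0.60 with 100, for S = 5 and 10), but the target is coverage of actual residents, so the correction belongs.
- **The wording is ambiguous.** The reference to sero-survey participants could instead restrict who is analysed. The source of coverage would then be unstated and surveillance cases outside the sero-survey would be dropped, so the sentence needs rewriting either way.

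Section 3 mentions recording vaccination status for possible cases and comparing it with a subset. That describes the case-cohort analysis and does not cancel the household form.

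**Conclusion.** The point holds as a low-severity improvement. As worded, the plan estimates its key explanatory variable from a 15.6% sample while already collecting vaccination status for household members generally, and the resulting sampling error attenuates the coverage slope in expectation.

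At 20% coverage the slope retained is about 60% to 86% with 30 blocks and 31% to 64% with 100 blocks, for a true between-block SD of 5 to 10 points. Both the number of blocks and the SD are assumptions, so the documents cannot settle where between minor and severe the loss falls. The figures cover sampling error only. They do not include proxy-report error or confounding between blocks, and they do not show that the final estimate must be too low.

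**What to change.** 1. State the number of housing blocks, and rewrite the sentence in Section 7.1 to say where coverage comes from and who is analysed.
2. Compute time-updated block coverage from the vaccination status of all enrolled members on the two-weekly household follow-up form, linked through the block code in the member ID.
3. Estimate overall effectiveness from block coverage, adjusting for age and sex but not conditioning on own vaccination status, with variance clustered by block. Alternatively, standardise from a model that includes own status. With own status held fixed, the coverage coefficient describes indirect protection, which is not the overall effect that Section 7.1 defines; report that model separately as the indirect effect.
4. Compare household-reported status with the sero-survey vaccination records for the same people, as a validation check or sensitivity analysis. If sample-based coverage is kept anywhere, apply a measurement-error correction.

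Cost: changes to the analysis text and some data linkage, with no new data collection. The main downside is reliance on reports by household heads, often by phone, which step 4 is meant to check.
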